5.1 Study Population Size

To ensure the study is adequately powered, up to 150 subjects will be enrolled at up to 7 centers in the US. The estimation of this sample size has taken into account the prevalence of suboptimal transtemporal windows and potential dropouts.

Once the 150 TTE subjects are enrolled, the study will continue to enroll up to another 150 subjects that received a TTE or TEE until enough TTE subjects have been enrolled in the different grades of the International Consensus Criteria (0,1,2,3) across the TTE Main Study and TTE/TEE Sub Study combined.

5.2 Study Duration

The enrollment period will last up to 15 months. Subject's participation in the study will last from 1 to 60 days.

The study will be complete when all subjects have been enrolled and all data collected. The study can be terminated at any time, for any reason, by NovaSignal. Should this occur, the study investigator will be notified as soon as possible. The Principal Investigators will be responsible for informing their IRBs of the termination of the trial.

5.3 Study Entry Criteria – TTE Main Study

5.3.1 Inclusion Criteria

A subject must meet all of the following inclusions criteria to be enrolled in the study:

- 1. Subject 18 years of age and older.
- 2. Subject presents with a clinical condition characterized by neurological signs and symptoms that, in the opinion of the investigator, include embolic stroke or TIA in the differential diagnosis.
- 3. Scheduled for a transthoracic echocardiograph (TTE) study with agitated saline contrast (bubble study) within ±30 days of informed consent.
- 4. Subject is able to successfully perform a Valsalva Maneuver (VM).
- 5. Subject or Legally Authorized Representative has the ability to provide informed consent and comply with the protocol.

5.3.2 Exclusion Criteria

A subject cannot be enrolled in the study if any of the following exclusion criteria are met:

DWF-C0001-001 CONFIDENTIAL Page 19 of 44

- 1. Subject has undergone an RLS/PFO closure.
- 2. Female who is pregnant or lactating at time of admission
- 3. Subjects who underwent partial or full craniotomy/craniectomy within the past 6 months.
- 4. Subjects who have a physical limitation preventing TCD/Headmount placement.

5.4 Study Entry Criteria – TTE or TEE Sub-Study (after first 150 subjects with TTE enrolled)

5.4.1 Inclusion Criteria

A subject must meet all of the following inclusions criteria to be enrolled in the study:

- 1. Subject 18 years of age and older.
- 2. Subject presents with a clinical condition characterized by neurological signs and symptoms that, in the opinion of the investigator, include embolic stroke or TIA in the differential diagnosis.
- 3. Scheduled for a transthoracic echocardiograph (TTE) or transesophageal echocardiograph (TEE) study with agitated saline contrast (bubble study) within ±30 days of informed consent.
- 4. Subject is able to successfully perform a Valsalva Maneuver (VM).
- 5. Subject or Legally Authorized Representative has the ability to provide informed consent and comply with the protocol.

5.4.2 Exclusion Criteria

A subject cannot be enrolled in the study if any of the following exclusion criteria are met:

- 1. Subject has undergone an RLS/PFO closure.
- 2. Female who is pregnant or lactating at time of admission
- 3. Subjects who underwent partial or full craniotomy/craniectomy within the past 6 months.
- 4. Subjects who have a physical limitation preventing TCD/Headmount placement.

6 STUDY PROCEDURES

6.1 Informed Consent and Screening

Subject identification and eligibility will be determined by the PI or study team based on their clinical assessment of the potential subject while that patient is undergoing standard of care for their condition.

Before participation in the study, candidates who may be eligible for the study will be provided with an informed consent according to 21 CFR 56 and 45 CFR 160-164 and guidelines of the Investigational Review Board of the institution at which the study is being conducted. Candidates will be given time to review the consent form and ask questions about the study. The investigator or delegated study staff is responsible for obtaining written informed consent from each potential study participant. Informed consent should be obtained, when required, in written format and using a form approved by the local IRB.

The subject must receive a copy of the signed and dated informed consent if requested. Waivers of consent will not be utilized in this study. The candidate or legal representative must sign the

DWF-C0001-001 CONFIDENTIAL Page 20 of 44

consent form prior to enrollment. Candidates will also be required to sign a Health Insurance Portability and Accountability Act (HIPAA) form which includes a Privacy Rule. This rule gives special safeguards to Protected Health Information (PHI) that is identifiable or can be directly linked to the subject (e.g., social security number, name, birth date). This authorization may be part of the informed consent form or separate. If applicable to the investigator site location, candidates will also be required to sign the California Experimental Subject Bill of Rights.

A subject will be considered enrolled at the time of Informed Consent signature.

6.2 Numbering of Study Subjects

Each site will be assigned a site number at the beginning of the study and each enrolled subject will be assigned a subject number. The subject number will consist of the study number, the site number followed by a sequential number that begins with "001".

6.3 Screen Failures

Subject eligibility will be determined by the PI or study team based on their clinical assessment of the potential subject while the patient is undergoing standard of care assessments for a stroke in the hospital.

For this protocol, a single measurement is defined as a collection of data at a single depth on a single side of the head. A scan is defined as a set of measurements which occur during a single data collection session and can include multiple measurements. A bilateral scan refers to measurements which are collected on each side of the head.

Subjects will be measured with NB-IS TCD and the de-identified data will be reviewed to determine the quality of the data for analysis. Subjects are considered evaluable if their NB-IS TCD data is of adequate quality and a complete data set is acquired. An adequate, evaluable, and complete study is defined for the purposes of this protocol as successful acquisition of a unilateral signal at 40-65mm depth range recorded for the duration of the bubble study in the Resting position and with Valsalva Maneuver. If the scan quality is adequate, the subject study data (via eCRF) and imaging will be collected and the NB-IS TCD utilized for analysis of the study endpoints. If the scan quality is inadequate, all subject clinical and imaging data will not be included in the final analysis.

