6.12.5 Transthoracic Echocardiography Procedure (TTE) per SOC

The TTE bubble study can be performed per standard of care within ±30 days of informed consent.

The following data points will be collected for the TTE procedure:

- Transthoracic Echocardiography (TTE) local results (SOC)
 - Date/Time of TTE bubble study
 - TTE Start/stop times with and without VM (as applicable)
 - Saline/Air Injection(s) Start/Stop time(s) with and without VM (as applicable)
 - Local Positive/Negative results for RLS/PFO
 - Local Bubble Count (as applicable)
 - Local TTE grading (as applicable)

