11.5 RLS/PFO Validation and Analysis

Evaluation of correlation between diagnostic imaging standard of care (SOC TCD/TTE/TEE) and NB-IS TCD diagnostic performance by an independent core laboratory. Success criteria will include clinical validation of NB-IS TCD for RLS/PFO detection targeting (i) 40% increase in NB-IS TCD sensitivity compared to TTE sensitivity and (ii) NB-IS TCD sensitivity ≥ 90% compared to SOC TCD sensitivity.

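### An inadequate NB-IS scan removes an enrolled subject from the primary comparison with TTE, with no matching TTE rule and no all-attempted analysis, so the gain applies only where NB-IS worked

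*Combined protocol and SAP*

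**What the plan says.** Section 6.3 defines the analysable subject by the investigational scan: "Subjects are considered evaluable if their NB-IS TCD data is of adequate quality and a complete data set is acquired". Completeness is then described through the NB-IS signal alone: one side, 40-65 mm depth, at rest and with Valsalva. The consequence of failing is explicit: "If the scan quality is inadequate, all subject clinical and imaging data will not be included in the final analysis". The preceding sentence links collection to the same condition: "If the scan quality is adequate, the subject study data (via eCRF) and imaging will be collected and the NB-IS TCD utilized for analysis".

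Although the section is headed Screen Failures, these subjects are past screening. Section 6.1 says "A subject will be considered enrolled at the time of Informed Consent signature", and the scan comes later.

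For TTE, section 6.12.5 says "The TTE bubble study can be performed per standard of care within ±30 days of informed consent". The local result is recorded as "Local Positive/Negative results for RLS/PFO", with no non-diagnostic category listed. Section 11.4 lets core-lab readings override local ones but sets no TTE adequacy rule. By contrast, section 6.12.4 gives a criterion for adequate Valsalva effort on NB-IS.

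Success criterion (i) in section 11.5 is a "40% increase in NB-IS TCD sensitivity compared to TTE sensitivity". NB-IS failures appear only in the secondary endpoints of sections 4.2 and 11.2 (no-window rate, success rate).

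**The concern.** The objective in section 4 is the shunt detection rate of NB-IS relative to standard-of-care tests, and section 2.4 presents TCD as a screening tool. For a patient sent for shunt work-up, an NB-IS session that finds no usable signal detects nothing, while the TTE in the same patient may be positive. Dropping that patient removes a possible pair in favour of TTE and never one in favour of NB-IS.

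The no-window and success rates show how many sessions failed, but not what TTE found in those subjects. A reader cannot rebuild the comparison for the whole referred population from them. The exclusion is also decided by the performance of the device under test, after enrolment, with no corresponding filter on the comparator.

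**Working it through.** **Inputs (section 11.6).** Sensitivity 0.90 for TCD and 0.50 for TTE; discordant proportion 0.50; prevalence 0.30; two-sided McNemar test at 0.05. Suboptimal temporal windows: 5% to 14% across the groups cited. Allowance for poor windows: 20% (100 to 120).

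**The plan's own figure.** The discordant cells sum to 0.50 and differ by 0.40, so they are 0.45 and 0.05. With 0.30 × 100 = 30 shunt-positive subjects, exact McNemar power is 0.8999; the table gives 0.89995. The plan's calculation reproduces.

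**Gain when failures count as not detected.** Let f be the share of NB-IS scans that fail among subjects with a shunt. If failure is independent of the TTE result, NB-IS sensitivity becomes 0.90 × (1 − f) and TTE stays at 0.50.

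- f = 5%: 0.90 × 0.95 = 0.855; gain 35.5 points
- f = 14%: 0.90 × 0.86 = 0.774; gain 27.4 points
- f = 20%: 0.90 × 0.80 = 0.720; gain 22.0 points

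Under the rule in section 6.3 the gain stays at 40 points whatever f is. The excess is 0.90 × f: 4.5, 12.6 and 18.0 points.

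**If TTE also does worse in these subjects.** Hold the evaluable-subject values at 0.90 and 0.50, and let t be TTE sensitivity in the failed-scan subjects. The all-attempted gain is (1 − f) × 0.40 − f × t, so the excess is f × (0.40 + t). At the extreme t = 0 the excess is still 2.0, 5.6 and 8.0 points. The size shrinks, but the direction does not change.

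**Against criterion (i).** Section 11.6 works with an absolute difference of 40 points, and 35.5, 27.4 and 22.0 all fall short of it. Read as a relative increase, the threshold is 0.50 × 1.4 = 0.70; 0.855, 0.774 and 0.720 all pass, and failure begins above f = 1 − 0.70/0.90, about 22%.

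**On the detection-rate scale.** Counting true shunts only, at 30% prevalence, the gain over all subjects moves from 0.30 × 40 = 12.0 points to 10.7, 8.2 and 6.6.

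**Power if the all-attempted analysis governed.** The discordant cells become 0.45 × (1 − f) and 0.05 × (1 − f) + 0.50 × f. At N = 144 (43 with shunt), exact power falls from 0.981 at f = 0 to 0.924, 0.679 and 0.458.

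**Collection, section by section.** Section 6.3 ties collection to an adequate scan. Section 6.5.1 marks TTE as required with no such condition. Section 8.2 asks for adverse event assessment in one paragraph for subjects with adequate data and in the next for all subjects scanned. Section 11.2 reports failed registrations and signals not found, which needs data on the failures. These do not fit together.

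**The case against.** The strongest reply is that the evaluable-only comparison is the stated design. Section 5 plans for evaluable subjects, section 5.1 says the size allows for poor windows, and section 11.1 frames the endpoint as diagnostic accuracy. An excluded subject loses both test results, so the paired contrast among evaluable subjects is internally valid. That stands: this is a choice of target population, not an error of calculation, and the evaluable-only result should be kept.

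It also stands that the failure rates used above may be too high. The 5% to 14% is the prevalence of suboptimal windows, whereas exclusion for want of a signal requires that neither side be usable. The 20% is a sample-size allowance, not a forecast.

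Two stronger inferences are tempting, and the documents support neither:

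- A reader might infer that TTE data of failed-scan subjects are never obtained, so that the effect could not be examined later. Section 6.3 does not write that data are collected only after an adequate scan. TTE is standard of care and required by the schedule, and section 12.3 gives access to subject records. The text shows a conflict, not proof of missing data.
- A reader might infer that a poor TTE is kept and scored negative. No section says how a non-diagnostic TTE is scored. The documents give no rate of such studies, so I put no figure on this.

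**Conclusion.** The point holds as one of scope and missing analysis. As written, the primary gain over TTE is conditional on NB-IS having worked, and it overstates the gain for the population sent for shunt work-up. The plan offers nothing that would show by how much.

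With the plan's design values the overstatement is 4.5 to 18.0 points for assumed failure rates of 5% to 20%, given independence from shunt status and TTE result. It is smaller if fewer scans fail or if TTE also does worse in these subjects. Whether this would change the outcome on criterion (i) depends on how the 40% is read: missed in all three scenarios as absolute points, met in all three as a relative increase. The documents do not support calling the evaluable-only contrast itself invalid.

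**What to change.** 1. In section 6.3, state that eCRF data and TTE/TEE results and images are collected for every subject with an attempted NB-IS scan, and reconcile sections 6.5.1, 8.2 and 11.2 with this.
2. Keep the evaluable-only comparison as the powered analysis for criterion (i). The power figures above show why the all-attempted analysis should not take that role at the present sample size.
3. Beside it, prespecify a comparison of paired detection rates in all subjects with an attempted NB-IS scan and a completed TTE, scoring failed or stopped NB-IS scans as not detected. Label it detection, not sensitivity: in failed scans shunt status is known mainly from TTE, since TEE and SOC TCD are collected only if performed. A detection rate also counts any false positive from either test.
4. Have the core lab, which already reads all TTEs, flag TTE adequacy (diagnostic quality, Valsalva performed). State how a non-diagnostic TTE is scored, and report the evaluable-only comparison also restricted to adequate TTEs.

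Cost: protocol wording, an adequacy field, one or two tables, and extra TTE transfers (5% to 20% of 150 is about 8 to 30 subjects in the main study). The downside for the sponsor is a less favourable NB-IS figure in the all-attempted analysis.

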6.7 NeuralBot Investigational System (NB-IS) Scanning Technique

The NB-IS TCD scanning session will consist of an initial set-up and signal search (up to 20 minutes). During this time, the system will search for CBFV signals at depths between 40-65 mm. Once the signal is acquired, the system can monitor the signal for up to 1 hour. In this study, once

the MCA signal has been acquired unilaterally or bilaterally, subjects will be monitored for up to 20 minutes during the delivery of the contrast agent at Rest and with Valsalva Maneuver.

The head cradle of the NeuralBot Investigational System is positioned underneath the subject's head and secured to a fixed location (bed, chair, or gurney). The user will affix two registration dots on each side of subject's temples. The subject's head is then positioned into the head cradle. The TCD modules are aligned to the head such that the probes are in contact with the subject's temples (temporal window). The user will register the Headmount to the subject's specific head shape and size. The user will apply gel to improve signal quality. The NeuralBot Investigational System will collect data and indicate to the user the scan status.

Subjects will be evaluated during the scanning period per ALARA ("As Low As Reasonably Achievable") criteria. Scanning may not violate ALARA levels and will be immediately terminated if ALARA criteria reached during a scanning session.

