6.8 ALARA Considerations

ALARA Considerations: "As Low As Reasonably Achievable – ALARA" principle for ultrasound to reduce the amount of total exposure to the subject without compromising exam quality.

Diagnostic ultrasound, including TCD, has been used clinically and in research for decades. In addition to the FDA guidance, there are several groups including the American Institute of Ultrasound in Medicine (AIUM), British Medical Ultrasound Society (BMUS), and the World Federation for Ultrasound in Medicine and Biology (WFUMB) that make recommendations on ultrasound safety for both fetal and non-fetal applications. These groups have focused on several areas of ultrasound safety including Thermal Index (TIC).

The FDA specifically references the AIUM for the ALARA recommendations for TIC and corresponding scan durations in the new guidance released in October 2017. Table 1 shows the recommended scan duration for a given TIC range. The ALARA recommendations are based on the TIC output by the device (which is displayed on the Lucid M1 System device at all times). TIC is defined as:

TIC – the thermal index for applications in which the ultrasound beam passes through bone near beam entrance into the body.

Thermal Index (TIC)	Recommended Duration (minutes)
>6.0	0
5.0-6.0	0.25
4.0-5.0	<1
3.0-4.0	<4
2.5-3.0	<15
2.0-2.5	<60
1.5-2.0	<120
<1.5	No Limit

DWF-C0001-001 CONFIDENTIAL Page 23 of 44

Table 1 - Recommended maximum exposure duration and TIC ranges (except the eyes which are not evaluated in this protocol)

If a subject meets ALARA criteria at any time during a scanning session, the scan will be discontinued.

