11.2 Secondary Technical Efficacy Endpoint(s) Analysis

- % detection of false positives (FP), comparison of NB-IS TCD with TTE
- % detection of true negatives (TN) (specificity), comparison of NB-IS TCD with TTE
- % detection of false negatives (FN), comparison of NB-IS TCD with TTE
- Positive Predictive Value (PPV), comparison of NB-IS TCD with TTE
- Negative Predictive Value (NPV), comparison of NB-IS TCD with TTE
- Demonstration of NB-IS TCD diagnostic performance to SOC TCD for diagnostic accuracy parameters (sensitivity, specificity, PPV, NPV).
 - o If bilateral signals are found, the microbubble count will be sum across both vessels.
 - o If only a unilateral signal is found, the microbubble count will be doubled for the total count.
 - Spencer Logarithmic Scale (SLS) and International Consensus Criteria (ICC) gradings from the Imaging Core Lab for NB-IS TCD and SOC TCD will be compared for analysis.
- Demonstration of NB-IS TCD diagnostic performance targeting to transesophageal echocardiography (TEE) for diagnostic accuracy parameters (sensitivity, specificity, PPV, NPV).
- % detection of intervenable shunts, comparison of NB-IS TCD with TTE
 - For NB-IS TCD, Grade 3 and above (>30 microbubbles) on the Spencer Logarithmic Scale (SLS) and International Consensus Criteria (ICC) considered intervenable shunt¹⁰.
 - o For TTE, >20 microbubbles per 2016 American Society of Echocardiography Guidelines and Standards²³ considered intervenable shunt.
- NB-IS TCD No Window rate performance to SOC TCD parameters (including both unilateral and bilateral absent acoustic windows).
- % success rate of NB-IS TCD
 - o Incidence of failed registrations (device unable to register)
 - Incidence of bilateral signals not found (no evaluable signals found both sides)
 - Incidence of unilateral signals not found (evaluable signal found on one side)
 - An adequate, evaluable, and complete study is defined for the purposes of this protocol as successful acquisition of a unilateral signal at 40-65mm depth range recorded for the duration of the bubble study in the Resting position and with Valsalva Maneuver.
- Incidence of device malfunctions

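### Applied as written, the section 6.3 exclusion makes NB-IS success 100% and failed registration and bilateral absence 0%, because section 11.2 states no denominator for them

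*Combined protocol and SAP*

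**What the plan says.** Section 6.3 calls a subject evaluable when the NB-IS data are adequate and complete. The minimum is a signal on one side, at 40-65 mm depth, recorded throughout the bubble study both at rest and with Valsalva. For scans that fall short, the rule is: "If the scan quality is inadequate, all subject clinical and imaging data will not be included in the final analysis". No endpoint is exempted.

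Section 11.2 then lists device-performance endpoints:

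- "NB-IS TCD No Window rate performance to SOC TCD parameters", covering unilateral and bilateral absence;
- the success rate, with three components: "Incidence of failed registrations (device unable to register"; "Incidence of bilateral signals not found (no evaluable signals found both sides"; and "Incidence of unilateral signals not found (evaluable signal found on one side".

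Under the success rate it repeats the definition from 6.3: "An adequate, evaluable, and complete study is defined for the purposes of this protocol as successful acquisition of a unilateral signal". It names no analysis set or denominator for any of these.

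On safety, section 8.2 has one paragraph that assesses subjects with adequate-quality data and another that assesses everyone scanned. Section 11.7 bases the safety assessment on device-related events collected throughout the study and sets no condition on scan quality.

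**The concern.** The endpoints under success rate exist to count scans that did not work. Section 6.3 removes exactly those subjects from the final analysis, using the same definition of adequacy. If the rule is followed as written, the success rate and the bilateral part of the no-window rate cannot show a device failure.

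This matters because usability is part of the study objective (section 4) and the device is meant to give consistent data independent of the user's experience (section 2.5). Success and no-window rates are the direct evidence on that. Without a stated denominator, the choice between enrolled subjects (section 6.1, at consent), scanned subjects (section 8.2) and evaluable subjects (section 6.3) could also be made after the failure counts are known.

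**Working it through.** **Plan figures.** The plan states no NB-IS failure rate and no expected success rate, so there is no figure of its own to reproduce on this point. Its main design figure, power 0.89995 at N = 100 in section 11.6, does reproduce: exact McNemar test, 100 × 0.30 = 30 shunt-positive subjects, discordant proportions 0.45 and 0.05. It does not bear on this question.

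**Step 1: who is removed.** A failed registration gives no signal. Bilateral absence gives no signal on either side. Neither can meet a definition that needs at least one side, so 6.3 removes both. A scan stopped before the rest and Valsalva recordings are complete is also removed, and section 6.8 provides for such stops: "If a subject meets ALARA criteria at any time during a scanning session, the scan will be discontinued". A subject with a signal on one side only can still be adequate and stays in.

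**Step 2: consequence.** With N attempted scans and f failures, n = N − f are evaluable.

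- Success over attempted scans: n/N. Under 6.3: n/n = 100%.
- Failed registration and bilateral absence under 6.3: 0/n = 0%.
- Unilateral absence, u subjects: u/N over attempted scans, u/n under 6.3.

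**Step 3: illustration.** Assumptions: N = 150 (the TTE Main Study); f = 8, 21 or 30, about 5%, 14% and 20%; u = 15. The first two rates are the lowest and highest suboptimal-window prevalences in section 11.6, and 20% is its sample-size allowance. They only set a range and are not expected failure rates of this device. Intervals are exact 95%.

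| f | n | Success over attempted | Success under 6.3 | Unilateral, over attempted | Unilateral, under 6.3 |
|---|---|---|---|---|---|
| 8 | 142 | 142/150 = 94.7% (89.8-97.7) | 142/142 = 100% | 15/150 = 10.0% | 15/142 = 10.6% |
| 21 | 129 | 129/150 = 86.0% (79.4-91.1) | 129/129 = 100% | 15/150 = 10.0% | 15/129 = 11.6% |
| 30 | 120 | 120/150 = 80.0% (72.7-86.1) | 120/120 = 100% | 15/150 = 10.0% | 15/120 = 12.5% |

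**Step 4: comparison with SOC TCD.** The exclusion depends on NB-IS quality only. Assume that every NB-IS failure is bilateral absence, that everyone has SOC TCD, and that SOC TCD also fails in f subjects, j of them the same people. In the analysed set NB-IS shows 0/n and SOC TCD shows (f − j)/n.

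- Independent failures: j = f²/N. For f = 21, j = 441/150 = 2.94 and (21 − 2.94)/129 = 14.0%. In the same way, f = 8 gives 5.3% and f = 30 gives 20.0%. NB-IS shows 0% each time, although the true rates are equal.
- Full overlap: j = f, so SOC TCD also shows 0% and there is no bias.

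**Step 5: safety.** Failed scans still expose the subject to the device: "The NB-IS TCD scanning session will consist of an initial set-up and signal search (up to 20 minutes". The all-scanned paragraph of 8.2 covers these subjects, and 11.7 uses events without regard to scan quality. Two passages leave a doubt: the general sentence in 6.3, and the paragraph of 8.2 that mentions adequate quality.

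**The case against.** The strongest reply is that the literal reading empties the endpoints of meaning. A failed registration can only be counted among attempted scans, so 11.2 shows what was intended. Also, 6.3 speaks of clinical and imaging data, while section 6.12.4 lists device deficiencies and technical observations as separate items. Both points have weight: a reader might infer that the sponsor plans to report 100% success, and the documents do not support that. But an inferred intent is not a prespecified denominator. No text places device observations outside 6.3 or says that 11.2 overrides it.

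A reader might also infer that the SOC TCD comparison is biased towards NB-IS. The documents do not establish this. SOC TCD is optional in the Schedule of Assessments, and both tests need an acoustic window in the same head, so independent failures are an extreme case. What stands is that a bias is possible, and that its size depends on the overlap.

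The third tempting inference is that adverse events in failed scans will be left out of the safety result. Sections 8.2 and 11.7 point the other way. If no events occur, dropping failed scans would not flatter the device either: the exact upper limit, 1 − 0.025^(1/n), rises from 2.4% for 0/150 to 3.0% for 0/120. Only a clarification is needed.

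**Conclusion.** The conflict between 6.3 and 11.2 is real and should be fixed. It is a stated rule that gives an uninformative result: 100% success and 0% failed registration and bilateral absence, by construction. It also shrinks the denominator for unilateral absence. In the illustration, success is overstated by 5.3, 14.0 or 20.0 percentage points; the true size depends on a failure rate that the plan does not give.

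The reach is limited. The affected efficacy endpoints are secondary, and neither success criterion in the Synopsis or section 11.5 depends on them. The point does not challenge the use of evaluable scans for the paired accuracy analyses. The SOC TCD effect is conditional, and the safety part is a matter of clarity. The statement that no denominator is given rests on the readable text; section 6.14 (study workflow) shows only a heading.

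**What to change.** 1. In 6.3, limit the exclusion to the paired diagnostic accuracy analyses.
2. In 11.2, use all subjects in whom an NB-IS scan was attempted, including failed registrations and scans stopped early, as the denominator for success rate, failed registrations, and unilateral and bilateral no-window rates, with the last two reported separately.
3. For the no-window comparison, use attempted subjects who also had SOC TCD.
4. Add one line that the safety endpoints include all scanned subjects, and that neither 6.3 nor the adequate-quality paragraph of 8.2 limits this.

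The cost is mainly wording, since most of the data are already collected; no visit or procedure is added. The success, failed-registration and bilateral figures may become less favourable to the device, while the unilateral rate may fall slightly. Keeping TTE results for failed scans, or adding a supporting primary analysis that counts failed scans as not detected, is optional and not needed to settle this point.
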